8.1.5.2 IGA Missing Data Imputation

A similar procedure will be used for the analyses based on proportion of IGA successes wherein the ANCOVA analysis is replaced with a logistic regression analysis. Specifically, missing IGA values from which the dichotomized IGA is derived will be estimated by MCMC.

The pattern of missing observations in each treatment group cannot influence the missing value estimation in the other because the imputation is being conducted independently for each treatment group.

The missing IGA values will be derived for the analysis using the method of MCMC multiple imputation. Multiple imputation and subsequent analysis will involve 3 principal tasks:

1. Create a data set, one for each treatment group, of patients with observed values and those needing estimation by MCMC. The missing IGA values in each data set will be filled in using the MCMC method 5 times to generate 5 data sets. The resulting data sets for each treatment arm will be combined into one complete data set by imputation.

Syntax:

```
proc mi data=datain out=dataout seed=&seed. nimpute=5 <options>;  
  where trtpn=(1, or 2);  
  mcmc chain=multiple;  
  var baseline week2 week4 week8 week12;  
run;
```

2. For each complete data set, the dichotomous success rate (clear or almost clear) will be computed. The estimated global values will be rounded to the nearest integer value prior to evaluating the success rate. Each complete data set will be analyzed with a logistic regression with factors of treatment group and analysis center.
3. The results from these analyses will be combined into a single inference using SAS PROC MIANALYZE.

A total of 2 random seeds will be needed to impute IGA for the two treatment groups. Those 2 random seeds have been pre-specified by using a random number generator:

- IGA Week S5G4T-1: Seed = 325011659
- IGA Week Vehicle: Seed = 1440479769

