19.4.7.2. IGA Missing Data Imputation

A similar procedure will be used for the analyses based on proportion of IGA successes wherein the ANCOVA analysis is replaced with a logistic regression analysis. Specifically, missing 12 week IGA values from which the dichotomized IGA is derived will be estimated by (MCMC). The pattern of missing observations in each treatment group cannot influence the missing value estimation in the other because the imputation is being conducted independently for each treatment group.

The missing 12-week IGA values will be derived for the analysis using the method of Markov Chain Monte Carlo (MCMC) multiple imputation. Multiple imputation and subsequent analysis will involve 4 principal tasks:

1. Create a data set, one for each treatment group, of patients with observed values and those needing estimation by MCMC. The missing IGA values in each data set will be filled in using the MCMC method 5 times to generate 5 data sets. The resulting data sets for each treatment arm will be combined into one complete data set by imputation.
Syntax:

```
proc mi data=datain out=dataout seed=&seed. nimpute=5
  <options>;
  where trtpn=(1, or 2);
  mcmc chain=multiple;
  var baseline week2 week4 week8 week12;
run;
```

2. For each complete data set, the dichotomous success rate (clear or almost clear with a 2-point change from baseline) will be computed. The 12-week estimated global values will be rounded to the nearest integer value prior to evaluating the success rate. Each complete data set will be analyzed with a logistic regression with factors of treatment group and analysis center.
3. The results from these analyses will be combined into a single inference using SAS PROC MIANALYZE.

A total of 2 random seeds will be needed to impute IGA for the two treatment groups. Those 2 random seeds have been pre-specified by using a random number generator:

- IGA Week 12 S5G4T-1: Seed = 712066910
- IGA Week 12 Vehicle: Seed = 1200150465
- IGA Week 8 S5G4T-1: Seed = 1871392013
- IGA Week 8 Vehicle: Seed = 1866129897
- IGA Week 4 S5G4T-1: Seed = 301965746
- IGA Week 4 Vehicle: Seed = 812607204

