6. STUDY DESIGN

6.1 Overall Study Design

This study will be a randomized, double-blind, multicenter, parallel group, active- and vehicle-controlled pivotal study of the efficacy and safety of S5G4T-1 and its vehicle for the treatment of papulopustular rosacea for 12 weeks. Approximately 350 patients with moderate to severe rosacea (rated 3 or 4 on the 5-point IGA scale) will be enrolled at up to 28 sites. Patients in this randomized, double-blind, vehicle-controlled, parallel-group multi-center study will be randomly assigned in a 2:1 ratio to S5G4T-1 or vehicle, respectively. Subjects with severe rosacea who are appropriate for systemic treatment need to be counseled regarding their treatment options by the Principal Investigator.

Patients will receive once daily treatment with S5G4T-1 or vehicle cream for 12 weeks. After the screening period, qualified patients will be randomly assigned at the Baseline visit and treated for 12 weeks. Efficacy assessments will include facial inflammatory lesion counts and IGA assessment ranging from 0 (clear) to 4 (severe). Investigators will be provided with instructions for lesion counts to ensure consistency of procedure. Patient reported outcomes (PRO) will be assessed with the PAPSS (Patient Assessment of Papulopustular Rosacea Signs and Symptoms), PAPI (Patient Assessment of Papulopustular rosacea Impacts), and PGI-S (Patient Global Impression of Symptom Severity) that will be administered at Baseline, Weeks 2, 4, 8, and 12, or at early termination. In addition, the PGI-C (Patient Global Impression of Change), PGI-TS (Patient Global Impression of Treatments Satisfaction), and PGI-SE (Patient Global Impression of Treatments Side Effects) will be administered at Weeks 2, 4, 8, and 12, or at early termination [FDA Guidance 2009]. Safety will be assessed at all visits and will include monitoring local and systemic adverse events (AEs); the Investigator Cutaneous Safety Assessment rating of

erythema, dryness and scaling, and the Local Tolerability Assessments rating of itching and burning/stinging on a scale ranging from 0 (none) to 3 (severe).

Patients will return to centers for IGA, lesion counts, PRO questionnaire, Investigator Cutaneous Safety Assessment, and Local Tolerability Assessments at Weeks 2, 4, 8 and 12. AEs and concomitant medications will be assessed throughout the treatment period. A urine pregnancy test is required at Visit 1, 2, 4, 5, and 6 for all females of child-bearing potential.

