7. EFFICACY AND SAFETY ENDPOINTS

7.1 Efficacy Endpoints

7.1.1 Primary Efficacy Endpoints

There are two co-primary efficacy endpoints:

- Proportion of patients with the primary measure of success (clear or almost clear) in IGA relative to Baseline at Week 12
- Absolute change in inflammatory lesion counts from Baseline to Week 12

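### Missing IGA grades are imputed with a normal model and rounded before the success cut, which misstates success in imputed patients. The trial-level effect is small and mostly conservative, and a discrete imputation model would avoid it.

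*SAP*

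**What the plan says.** SAP section 7.1.1 states: "There are two co-primary efficacy endpoints". One is IGA success at Week 12. The scale has five ordered grades, 0 to 4, and patients enter "rated 3 or 4 on the 5-point IGA scale".

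For missing grades, SAP section 8.1.5.2 runs PROC MI separately in each arm with the statements "mcmc chain=multiple" and "var baseline week2 week4 week8 week12". There is no CLASS statement, so the grades enter as continuous variables in a multivariate normal model. The SAP then says "The estimated global values will be rounded to the nearest integer value prior to evaluating the success rate", and for each completed data set "the dichotomous success rate (clear or almost clear) will be computed". Protocol section 19.4.7.2 has the same rule for Week 12: "The 12-week estimated global values will be rounded to the nearest integer value prior to evaluating the success rate". Neither document gives a reason for treating the grade as normal.

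The imputed values feed the primary ITT logistic regression and the Week 8 and Week 4 IGA endpoints, steps 3 and 5 of the secondary testing sequence (SAP section 8.1.8).

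SAP section 8.7.2.2 plans two IGA sensitivity analyses without rounding: a GEE model with no imputation, and a logistic imputation of the binary outcome using treatment and analysis center only.

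**The concern.** Rounding to the nearest integer turns the success rule into a cut of a normal draw at 1.5. The normal model matches the mean and variance of the grades, but not the probability of grade 0 or 1, which is all the endpoint uses. The error depends on the shape of the grade distribution. If treatment works, that shape differs between arms, so the error need not cancel. At stake is an avoidable distortion of a co-primary response rate that grows with the fraction imputed.

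**Working it through.** **The plan's own figure.** SAP section 9 states 86 active and 43 vehicle patients for 95% power, 53.3% vs 20.0%, two-sided 0.05, 2:1. With pooled rate (0.20 + 2×0.533)/3 = 0.422 and difference 0.333, the vehicle n without continuity correction is

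[1.960×√(0.422×0.578×1.5) + 1.645×√(0.20×0.80 + 0.533×0.467/2)]² / 0.333² = 38.4, or 39 (78 active).

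With the continuity correction, 38.4/4 × [1 + √(1 + 6/(2×38.4×0.333))]² = 42.8, or 43 (86 active). The stated figure reproduces exactly, so 53.3% and 20.0% are used below.

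**Success definition.** Baseline is 3 or 4, so grade 0 or 1 is always a drop of at least two grades. The protocol's two-grade wording and the SAP's shorter wording coincide, and success means grade 1 or lower.

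**Marginal check.** For a patient with no post-baseline data, the rule gives a success probability of about Φ((1.5 − mean)/SD). Four Week 12 grade distributions per arm were assumed, each fixed at the planned success rate. Example, active shape C: grades 0 to 4 at 5%, 48.3%, 30%, 15% and 1.7%; mean 1.601, SD 0.861; Φ(−0.101/0.861) = 45.3%, against a true 53.3%.

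| Assumed shape | Active mean, SD | Active result (true 53.3%) | Vehicle mean, SD | Vehicle result (true 20.0%) |
|---|---|---|---|---|
| A | 1.571, 1.062 | 47.3% | 2.370, 0.956 | 18.1% |
| B (active bimodal) | 1.681, 1.257 | 44.3% | 2.420, 1.079 | 19.7% |
| C (active few clear) | 1.601, 0.861 | 45.3% | 2.180, 0.853 | 21.3% |
| D (active many clear) | 1.461, 1.237 | 51.3% | 2.460, 1.004 | 17.0% |

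**Check using earlier visits.** Baseline and Weeks 2, 4, 8 and 12 were simulated with 400,000 patients per arm, monotone dropout of 9.5% to 9.8%, missing completely at random or at random, and latent correlation 0.6 or 0.85. A multivariate normal model was fitted by arm, and the draws were rounded and cut. Over the 16 scenarios the error among imputed patients was:

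- active: −1.7 to −9.4 points;
- vehicle: −3.2 to +1.6 points.

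Conditioning on earlier grades therefore does not remove the error.

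**Effect on the treatment difference.** The shift is the missing fraction times (active error − vehicle error).

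- Largest loss (shape C, completely at random, correlation 0.6): 0.096 × (−7.7 − 1.2) = −0.85 points.
- Largest gain (shape D, at random, correlation 0.6): 0.096 × (−1.7 + 2.4) = +0.07 points.
- The difference shrank in 13 of the 16 scenarios.
- Doubling for about 20% missing gives about −1.7 to +0.15. Halving for 5% gives about −0.4 to 0.

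**Scale.** The standard error of the difference at 234 and 117 is √(0.533×0.467/234 + 0.20×0.80/117) = 0.0493, or 4.9 points. A shift of −0.85 is 0.85/4.93 = 17% of one standard error. Power at the planned effect stays above 99.9%.

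**Illustration at a smaller effect.** At an assumed 40% vs 25%, power is 80.5% with no shift. It is 79.2% if the active rate falls by 0.25 points and 75.7% if it falls by 0.9. Neither the smaller effect nor these shifts stand in the documents, and the 0.9 is carried over from the 53.3% scenarios.

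**The case against.** The case for leaving the method alone is substantial.

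- **It is partly checked already.** Both analyses in SAP section 8.7.2.2 avoid rounding. This stands as a partial check. However, the GEE model imputes nothing, and the logistic imputation drops each patient's baseline and earlier grades. If either disagreed with the primary result, rounding could not be separated from those other differences, and neither replaces the primary analysis.
- **It is small.** This stands at the trial level: under 1 point at about 10% missing, against a standard error of 4.9.
- **The size rests on assumptions.** This stands too, so only ranges are given. The protocol's study flow chart (section 13.9) asks early terminators to complete the Week 12 procedures, and SAP section 8.1.3 maps their data to an analysis visit. Patients with no post-baseline data should therefore be fewer than total dropout.
- **Some dropouts may never be rounded.** SAP section 8.1.5 resets certain discontinuations to the Baseline value after imputation. It is unclear whether this covers only the PP population or also ITT. The calculations do not include it.
- **A discrete model has its own difficulty.** Good grades may be sparse at early visits in the smaller vehicle arm. This stands, and the rule for it must be fixed in advance.

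A reader might infer that rounding favors the active product or creates false positives. The calculations do not support that: the error is mostly downward in the active arm. With no treatment effect, equal grade distributions and similar missingness, it is the same in both arms and cancels. A reader might also think that draws below 0 or above 4 corrupt the endpoint. They do not: the former is still a success and the latter still a failure. Only the by-grade tables could be affected.

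**Conclusion.** The point holds as a modest, cheap improvement. The stated rule gives a wrong and arm-dependent success probability for imputed patients: too low by about 2 to 9 points in the active arm and off by about -3 to +2 points in the vehicle arm. The treatment difference moves by about -0.85 to +0.1 points at 10% missing and about -1.7 to +0.15 at 20%. These ranges assume the planned 53.3% and 20.0%, the grade shapes and correlations listed, and dropout that is random or explained by observed data. The documents supply neither the grade distribution nor the dropout rate. The bias is mostly conservative, though not guaranteed to be so, since three scenarios showed a slight gain. It does not put the planned power at risk and is no reason to doubt the design.

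**What to change.** Make the primary IGA imputation discrete. Use PROC MI with FCS LOGISTIC, run by arm, with IGA as a class variable and baseline and earlier-visit grades as predictors. Derive success directly from the imputed grade, with no rounding. State in the SAP before unblinding what happens when grades are sparse or the logistic fit separates: for example, collapse adjacent grades without crossing the cut between 1 and 2, or impute binary success. Keep the normal-and-round version as a sensitivity analysis.

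The cost is a few lines of SAS, and section 8.7.2.2 already uses a class statement and logistic imputation for IGA. SAP section 2 allows updates until the blind is broken. The downside is slightly more programming and a possible need to collapse sparse grades.

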8.1.5.3 Medication Date Imputation

If the medication start date is incomplete, then it will be imputed as follows for the purpose of determining concomitant use:

- If the start date is completely missing, the start date will be equal to the first dose date. However, if the stop date is not missing and is before the first dose date, then the stop date will be used instead.
- If the start day is missing, the first day of the month will be used.

- If the start day and month are missing, then the first day of the first month (January) will be used.

If the medication stop date is incomplete, then it will be imputed as follows for the purpose of determining concomitant use:

- If the stop date is completely missing and the medication is not ongoing, the stop date will be equal to the last dose date or date of completion/withdrawal, whichever is the latest.
- If the stop day is missing, the last day of the month will be used.

If the stop day and month are missing, then the last day of the last month (December) will be used.

8.1.6 Interim Analyses and Data Monitoring

No interim analysis or data monitoring is planned for this study.

8.1.7 Multicenter Studies

The clinical study will be conducted under a common protocol for each investigational site with the intention of pooling the data for analysis. Every effort will be made to promote consistency in study execution at each investigational site. The study is intended to be conducted in a manner such that a minimum of 15 subjects will be randomized and included in the ITT population (i.e., at least ten subjects in the active treatment arm and five subjects in the vehicle treatment arm) for any investigator. In the event that there are too few subjects in a treatment arm for an investigational site, then the site's data will be combined with other site's data to achieve the desired sample size minimum per treatment arm. The combining of investigator data will be accomplished by taking the data of the investigator with the smallest enrollment and combining them with the data of the investigator with the largest enrollment, restricted to investigational sites which did not meet minimum enrollment. If there is a further need to combine data, then the data of the investigator with the second smallest enrollment will be combined with the site's data which had the second largest enrollment (restricted to investigational sites which did not meet minimum enrollment), and so on. This process will continue for all investigators who did not have a minimum of 15 subjects enrolled. The process of combining investigator data that have insufficient subjects per treatment arm will result in redefining the groups of investigators for the purposes of statistical analyses. These combined groups will be referred to as "analysis centers" in the statistical analyses.

The consistency of treatment response will be investigated across the analysis centers subsequent to combining the data as described above. Statistical tests will be conducted to identify if there are extreme analysis centers that could affect the interpretation of common statistical and clinical conclusions. An analysis center by treatment interaction will be included in the primary analyses to test for parallel treatment effect at an alpha level of 0.10. Change from Baseline in inflammatory lesions will be analyzed with an ANCOVA (unranked or ranked) with factors of treatment group, analysis center, and treatment group by analysis center interaction, and the Baseline lesion count variable as a covariate. For the purpose of testing consistency of treatment response, the dichotomized IGA will be analyzed with a logistic regression with factors of treatment group, analysis center, and the interaction term of treatment group by analysis center. Further examination will follow for any variables that have a significant ANCOVA or logistic regression interaction term.

In the event that the ANCOVA or logistic regression interaction (referred to henceforth as the “appropriate test”) p-value is less than or equal to 0.10, a sensitivity analysis that excludes analysis centers with the extreme efficacy result will be performed to determine the robustness of the treatment effect. On the other hand, if all three analyses result in interaction terms with p-values greater than 0.10, then the conclusions from the pooled data will be considered to be free of the impact of extreme analysis centers.

The first step in conducting a sensitivity analysis is to identify the extreme analysis center or centers that contribute to the statistical significance of the appropriate test. The process involves submitting subsets of analysis centers to the appropriate test and observing the appropriate test p-value for the subset. Subsets with p-values greater than 0.10 for the appropriate test are considered homogeneous.

The search for an extreme analysis center begins by analyzing all subsets that can be created by excluding one analysis center. If one or more of the subsets result in an appropriate test p-value greater than or equal to 0.10, then the analysis center excluded from the subset with the largest p-values for the appropriate test is deemed to be the extreme analysis center.

If all appropriate test subset p-values are less than or equal to 0.10, then the process will analyze the appropriate test for all subsets that can be created by excluding two analysis centers. If one or more of these subsets generate appropriate test p-values larger than 0.10, then the analysis centers excluded from the subset with the largest appropriate test p-value are deemed the extreme analysis centers.

Thus, the process of identifying the extreme analysis centers will continue in a stepwise manner by first excluding one, then two, then three, etc., analysis centers until the appropriate test p-value exceeds 0.10.

Once the extreme analysis center or centers have been identified, then the treatment p-values of the remaining analysis centers will be computed. Inferences will be drawn from the p-values as well as any pertinent observations regarding the extreme analysis center or centers. Additionally, it is noted that this process excludes patients from the analysis in a non-random manner and has an unpredictable impact on the power of the treatment effect test. In the event that the treatment effect of the remaining subset is not statistically significant, due consideration of the post-hoc aspects of the process will be given when the results are interpreted. Conclusions will be presented by the Sponsor as appropriate to the findings of the sensitivity analysis.

Prior to investigating the treatment effect within the analysis centers, the treatment effect within investigational site will be investigated to determine if the site-to-site variability is such that it could mask the analysis center effects. Thus, prior to pooling, change from Baseline in inflammatory lesions will be analyzed with an ANCOVA (unranked or ranked) with factors of treatment group, investigational site, and treatment group by investigational site interaction, and the Baseline lesion count variable as a covariate. The dichotomized primary endpoint will be analyzed with a logistic regression with factors of treatment group, investigational site, and the interaction term of treatment group by investigational site. If any of the analyses are not computationally feasible due to some investigational sites having very few subjects enrolled, the low-enrolling investigational sites will be excluded from the analysis.

8.1.8 Multiple Comparisons/Multiplicity

In testing the secondary efficacy endpoints the overall Type I error will be controlled by requiring the two co-primary efficacy endpoints to be statistically significant. Specifically, failure of either one of the primary efficacy endpoints will invalidate the statistical significance of the secondary efficacy endpoints.

A stepwise process will be conducted for testing the secondary efficacy endpoints in order to control for multiplicity. These tests will be performed for only the ITT population. The testing process will terminate whenever a statistical test for a step is not significant. All subsequent tests for the remaining steps will be considered not significant. The order of testing is provided below.

Step Number	Secondary Endpoint
1	Percent change in inflammatory lesion count from Baseline to Week 12
2	Absolute change in inflammatory lesion count from Baseline to Week 8
3	Proportion of patients with the primary measure of success “Clear” (0) or “Almost clear” (1) in the IGA relative to Baseline at Week 8
4	Absolute change in inflammatory lesion count from Baseline to Week 4
5	Proportion of patients with the primary measure of success “Clear” (0) or “Almost clear” (1) in the IGA relative to Baseline at Week 4

In testing the supportive efficacy endpoints, the overall Type I error will be controlled by the Benjamini-Hochberg method. The Hochberg and Benjamini adaptive step-down Bonferroni method will be used within PROC MULTTEST in SAS (AHOLM option in PROC MULTTEST).

